## Statistical Analysis

Our primary hypothesis is that vibrotactile CR stimulation (i) will improve the outcome measured as On-time at least by 30% compared to the baseline after three months of usage. We also expect that (ii) the relative increase in On-time in the intervention arm (using vibrotactile CR stimulation) will be at least 20% compared to the control arm (Sham) after three months of usage. In order to test these hypotheses, we will perform Welch's t-test (paired t-test for the first hypothesis and unpaired two-sample t-test for the second hypothesis). Our power analysis shows that the sample size of 10 patients for each arm will provide 85% - 98% of power for detecting statistically significant difference based on the mean On Time of 7.3 at baseline and SD of 2-2.5 that were obtained from our preliminary study.

**Based on this power analysis, we are planning to enroll a minimum of 60 patients. 30 patients will be randomized to receive the real stimulation initially. The remaining 30 will be randomized to receive sham stimulation, using dedicated sham stimulation pattern.**

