**Month 1- month 6 (daily, at home):**

- 2hr vibrotactile stimulation (CR vs sham), Session 1 morning
- 2hr vibrotactile stimulation (CR vs sham), Session 2 late afternoon
- Hauser diary to capture OFF time, ON time, ON time with troublesome dyskinesia, sleep time

Patients will return **at 3, 6 and 7 months** and will follow the same procedures as enrollment day 1 and 2

[figure not shown]
After the 6 month follow up, the patient will receive no stimulation for 1 month to asses long term effects and return at 7 months for a follow up assessment.

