#### Withdrawal

Each Subject, the Sponsor or its designee and the Investigator reserve the right at any time to terminate a Subject's participation in the clinical investigation.

Possible reasons for withdrawal from the study:

1. Subject voluntarily withdraws consent
2. Subject develops an Adverse Event (AE) that would not allow him or her to continue in the study
3. Subject has an AE which in the opinion of the Investigator warrants withdrawal from the study. Such an AE would include anything unexpected that requires hospitalization. The Sponsor or its designee must be notified within 2 business days
4. A decision is made by the Subject and/or Investigator that the Subject should be withdrawn from the study

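### Month-3 t-tests with no missing-data rule can bias the On-time effect if patients leave early; a mixed model on monthly diary means would use data the plan already schedules

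*Combined protocol and SAP*

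**What the plan says.** The Statistical Analysis section states two hypotheses on On-time at three months. The first is that CR "will improve the outcome measured as On-time at least by 30% compared to the baseline after three months of usage". The second is that the relative increase over control "will be at least 20% compared to the control arm (Sham) after three months of usage". The tests are a "paired t-test for the first hypothesis and unpaired two-sample t-test for the second hypothesis". The document has no separate analysis plan, and no section defines an analysis set, a missing-data or imputation rule, an expected dropout rate, or follow-up after withdrawal.

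The Withdrawal section foresees early leaving: "Each Subject, the Sponsor or its designee and the Investigator reserve the right at any time to terminate" a subject's participation.

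The Protocol summary lists, under the daily at-home heading for months 1 to 6, a "Hauser diary to capture OFF time, ON time, ON time with troublesome dyskinesia, sleep time". The Day 2 list adds a weekly call that includes a diary review. On-time is therefore recorded from the first month for everyone who starts.

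Two gaps matter for any remedy. The Day 0, Day 1 and Day 2 lists do not include a baseline diary. The Data collection section describes the diary as an electronic, wearable-based record rather than a Hauser diary.

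**The concern.** A paired t-test needs both values from each patient, and a two-sample test at month 3 needs the month-3 value. With no other rule, a patient who leaves in month 2 drops out of both tests, although several weeks of that patient's diary exist. ANCOVA at month 3 would lose the same patients, so this is separate from baseline adjustment.

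The regimen asks for two 2-hour sessions a day at home for six months. The Risks section accepts that stimulation might be uncomfortable or worsen symptoms, while sham delivers nothing. The Primary Hypothesis section expects benefit to show within a month, so a patient could judge the treatment and leave well before month 3. If those who leave differ in On-time from those who stay, completers no longer represent the randomised arms, and the comparison loses part of the protection of randomisation.

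**Working it through.** **Inputs from the Statistical Analysis section.** Mean and SD: "based on the mean On Time of 7.3 at baseline and SD of 2-2.5". Size: "we are planning to enroll a minimum of 60 patients. 30 patients will be randomized to receive the real stimulation initially", so 30 per arm. Hypothesis (i): 0.30 × 7.3 = 2.19 h. Hypothesis (ii): read as 0.20 × 7.3 = 1.46 h (the alternative, 20% of the CR mean after the gain, is 0.20 × 9.49 = 1.90 h).

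**Assumed, because the document does not say.** Two-sided 5% level; SD 2.25 (mid-range); within-patient correlation 0.4-0.6; all dropout rates and mechanisms.

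**The plan's own figure.** It says "the sample size of 10 patients for each arm will provide 85% - 98% of power". For hypothesis (i) with n = 10, a one-sided 5% normal approximation gives:
- SD 2: 2.19/(2/√10) − 1.645 = 1.82, power 96.6%
- SD 2.5: 2.19/(2.5/√10) − 1.645 = 1.13, power 87.0%

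This matches to within 2 points. So does a two-sided t-test with a baseline to month-3 correlation of about 0.67. Neither assumption is stated. For hypothesis (ii), 10 per arm gives 34% (SD 2) to 24% (SD 2.5) two-sided. That mismatch is a separate matter. What matters here is that no version of the calculation contains a dropout allowance. At 30 per arm, power for (ii) is 79% (SD 2) or 60% (SD 2.5) with complete data, and 70% or 51% if 20% have no month-3 value (24 per arm).

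**Bias, simulation A.** 500 trials per scenario. Gains of 10/20/30% (CR) and 5/8/10% (sham) at months 1/2/3. About 17-20% leave after month 1, depending on the month-1 change in one arm and at random (15%) in the other. True difference (30% − 10%) × 7.3 = 1.46 h. Monte Carlo SE about 0.03 h.

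| Poor responders leave | Completers (r = 0.4 / 0.6) | Error | Likelihood estimate |
|---|---|---|---|
| CR arm | 1.74 / 1.63 h | +0.28 / +0.17 h (+19% / +12%) | 1.47 / 1.44 h |
| Sham arm | 1.13 / 1.23 h | −0.33 / −0.23 h (−23% / −16%) | 1.43 / 1.45 h |

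The within-CR gain among completers rises from 2.19 h to about 2.4-2.5 h.

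**Bias, simulation B.** 1,500 trials per setting, correlation 0.6, true difference 1.46 h reached linearly by month 3, leaving after month 1 or 2, nominal dropout settings 10%, 20% and 30%. The likelihood estimate uses an unstructured covariance fitted by EM.

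| Leaving depends on | t-test on completers | Error | Likelihood estimate |
|---|---|---|---|
| Nothing (random) | 1.45-1.46 h | about 0 | 1.45-1.47 h |
| Observed diary change, both arms | 1.30-1.35 h | −0.16 to −0.11 h | 1.45-1.47 h |
| Observed diary change, CR only | 1.71-1.88 h | +0.25 to +0.42 h | 1.44-1.48 h |
| Unseen month-3 value, CR only | 1.72-2.00 h | +0.26 to +0.54 h | 1.64-1.84 h |
| Unseen month-3 value, both arms | 0.98-1.14 h | −0.48 to −0.32 h | 1.10-1.23 h |

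The settings are nominal. Where leaving depends on the diary, the share actually missing can be higher.

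**No true effect.** At the 20% setting with diary-dependent leaving in CR only (35% missing in CR, 20% in sham), the t-test averages +0.46 h and rejects in 12% of trials instead of 5%. The likelihood estimate averages −0.02 h.

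**If leaving is random.** At the 20% setting, approximate power is 70% for the t-test and 73% for the repeated-measures model.

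**Scale.** The SD of change is 2.25 × √(2 × 0.4) = 2.01 h, so with 24 per arm the standard error is 2.01 × √(2/24) = 0.58 h. An error of 0.1-0.4 h is about 0.2 to 0.7 standard errors.

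**The case against.** A reader might infer that the plan prescribes a complete-case analysis and throws diaries away. It does not say so. It is silent, and a t-test can follow multiple imputation. What stands against the plan is an omission whose default outcome is the loss of early leavers. Silence is no safeguard, because the choice would then be made after the data are seen.

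A reader might also infer that the effect will be biased. The document gives no dropout rate and no link between leaving and response, and with random leaving there is no bias. Nor does the difference in sensation between arms establish differential leaving: under Sham control, participants are told in advance that one of the two treatments should not be felt. That weakens the case for arm-specific leaving without excluding it.

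The diary-dependent scenarios favour a likelihood method by construction, since leaving depends on observed values. This objection is right, and the unseen-value rows show its force: the model's error there is +0.18 to +0.38 h or −0.36 to −0.23 h. It is smaller than the t-test's but far from nil.

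The simulated estimator is not exactly the model proposed. It was fitted by EM to baseline and three monthly means. An unstructured matrix over six months would need 6 × 7/2 = 21 covariance parameters from about 60 patients. Limiting the primary model to months 1-3 reduces this to 3 × 4/2 = 6.

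Finally, 60 patients might seem an ample reserve against the 10 per arm in the power statement. A larger sample offsets lost precision, not bias.

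**Conclusion.** The point holds as a risk from an unstated rule. As written, the month-3 tests would by default omit patients without a month-3 value and ignore their earlier On-time data, which can bias both the CR-sham contrast and the within-CR change, in either direction. When leaving depends on observed diaries, the error is about 0.1-0.4 h on a true 1.46 h, with 12% false positives in one null scenario. These sizes are illustrative: they rest on assumed dropout settings, correlations and leaving mechanisms.

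The documents do not support saying that the estimate is biased, or that a mixed model cures the problem in general. The model corrects for leaving explained by the observed diary, loses nothing if leaving is random, and is itself biased if leaving depends on values never seen. Nor are all the data it needs clearly planned: post-baseline diaries are scheduled, but no baseline diary is listed. The t-test of change from baseline needs that value too, so the gap is no reason to prefer it.

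This is a cheap improvement that should be made, and no ground to call the design unsound.

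**What to change.** In the Statistical Analysis section:

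- Make the primary analysis a mixed model for repeated measures on monthly mean diary On-time at months 1, 2 and 3, in all randomised patients by assigned arm; later months are secondary. Terms: baseline On-time, arm, month and arm-by-month. Use an unstructured covariance, a stated simpler fallback if it does not converge, and Kenward-Roger degrees of freedom.
- Take the month-3 CR-sham contrast for hypothesis (ii) and the month-3 within-CR change for hypothesis (i) from this model, so that neither hypothesis is lost and the time point stays at three months. State how the 20% and 30% translate into hours.
- Keep the paired and two-sample t-tests as sensitivity analyses.
- Add one delta-adjusted (missing-not-at-random) sensitivity analysis. Include patients who leave before giving any monthly mean, since the model cannot use them.

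Elsewhere in the protocol:

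- Confirm that a baseline diary is collected, and when.
- Reconcile the Hauser diary in the Protocol summary with the wearable-based diary in the Data collection section.
- Define the monthly mean, including the minimum number of valid diary days.

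The cost is a few paragraphs of text and a little programming, with no new post-baseline collection; a baseline diary must be added if none is planned. The downside is reliance on missing-at-random given the observed diary, which the delta-adjusted analysis is there to test. The change should be fixed before unblinding.

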Based on this study, we propose to deliver vibrotactile CR stimulation during a longer treatment period, in order to assess durability and efficacy vs. a sham vibrotactile approach. This study is designed to best assess vibrotactile CR stimulation compared to sham as an alternative to best medical therapy for Parkinson's disease. With our

project, we are hoping to establish a simple, non-invasive treatment that will provide ongoing relief with minimal side effects or inconvenience to the patient.

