#### Sham control

Parkinson's patients are particularly vulnerable to the placebo effect. The best method of reducing placebo effects in a placebo effect prone population is to blind the participants. In order to do this, sham participants will receive a non-stimulation (0 amplitude) chip that is inserted into the vibrotactile device. All participants will be told that they will receive 1 of two chips, 1 is regular vibrotactile reset and the other (sham) is called Stochastic resonance vibrotactile coordinated reset. The patient will learn that Stochastic resonance treatment is most effective when the patients vibratory stimulus threshold (i.e the minimum perception thresholds) is set as 90%. This means that the patient should not feel the vibrations on their fingers if they receive vibratory stochastic resonance. We will take vibrotactile threshold measurements from patients to make this story convincing and to add another dependent measure. If placed into the sham condition, the patient will receive no stimulation, however they will be convinced that they are receiving stimulation

Vibrotactile CR stimulation therapy system is a commercially available (though not yet FDA-approved), non-invasive, battery-operated mobile device. The device consists of a handheld component with vibro-tactile stimulators (tactors) and is fitted and programmed by a qualified healthcare professional familiar with Parkinson's disease treatment (e.g., physicians, advanced practice providers, nurses and/or their clinical research assistants).

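### One power range (85%–98% at 10 per arm) is given for two different tests; the stated inputs do not yield it for the sham comparison, and no power is given at the planned 30 per arm

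*Combined protocol and SAP*

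**What the plan says.** All of this is in the Statistical Analysis section of the combined protocol and SAP. It sets two hypotheses at three months.

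- (i) Stimulation "will improve the outcome measured as On-time at least by 30% compared to the baseline after three months of usage".
- (ii) Against sham, "the relative increase in On-time in the intervention arm (using vibrotactile CR stimulation) will be at least 20% compared to the control arm (Sham", again at three months.

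The tests are a "paired t-test for the first hypothesis and unpaired two-sample t-test for the second hypothesis". One power statement follows: a "sample size of 10 patients for each arm will provide 85% - 98% of power for detecting statistically significant difference". Its inputs are a baseline mean of 7.3 and an SD of 2–2.5, both taken from the sponsor's earlier work. The next sentence reads "Based on this power analysis, we are planning to enroll a minimum of 60 patients", split 30 and 30.

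The section does not give alpha, sidedness, the hours meant by 20%, whether the SD is of On-time or of its change, any within-patient correlation, a dropout allowance, or power at 30 per arm. No other section supplies them.

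**The concern.** A paired test on one arm and a two-sample test between arms have different standard errors, and here they also have different target effects. At the same n and SD they would not normally share one power range, so it matters which test the 85%–98% describes.

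The sham comparison is the one that carries the trial. The Background says "This study is designed to best assess vibrotactile CR stimulation compared to sham as an alternative to best medical therapy", and the Sham control section says that "patients are particularly vulnerable to the placebo effect". A gain from baseline within the active arm cannot separate treatment from placebo response; only (ii) can. A reader who sees power quoted for 10 patients in each arm will naturally take it as power for that comparison. If it is not, the plan has no power statement for (ii), the stated basis for 60 patients cannot be checked, and a null result against sham would be hard to interpret.

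**Working it through.** **Inputs from the Statistical Analysis section:** baseline mean 7.3; SD 2–2.5; 30% for (i); 20% for (ii); 10 per arm in the power statement; 30 per arm planned.

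**Assumed, because not stated:** On-time in hours; two-sided 5%; SD 2–2.5 applies to whatever variable is analysed. If 2–2.5 is instead the SD of On-time at one visit, the SD of change is SD × √(2(1−r)), and the assumption amounts to r = 0.5.

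**Differences in hours**
- (i): 0.30 × 7.3 = 2.19.
- (ii), 20% of baseline: 0.20 × 7.3 = 1.46.
- (ii), 20% of the improved mean: 7.3 + 2.19 = 9.49, and 0.20 × 9.49 = 1.90.
- (ii), sham unchanged and the full gain separating the arms: 2.19.

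**Formulas (noncentral t)**
- Paired: noncentrality = d / (SD/√n), df = n − 1.
- Two-sample: noncentrality = d / (SD × √(2/n)), df = 2n − 2.

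**Attempt to reproduce 85%–98% at 10 per arm**

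Test (i), SD 2: 2.19/(2/√10) = 3.46 on 9 df, power 86.8%. SD 2.5: noncentrality 2.77, power 69.4%.

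Test (ii), d = 1.46, SD 2: 1.46/(2 × √0.2) = 1.63 on 18 df, power 34%. SD 2.5: noncentrality 1.31, power 23.5%.

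| Test, difference | 10 per arm, SD 2.5 to SD 2 | 30 per arm, SD 2.5 to SD 2 |
|---|---|---|
| (i) paired, 2.19 h | 69%–87% | above 99% |
| (ii) two-sample, 1.46 h | 24%–34% | 60%–79% |
| (ii) two-sample, 1.90 h | 36%–52% | 82%–95% |
| (ii) two-sample, 2.19 h | 46%–64% | 92%–99% |

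The plan names Welch's test. A simulation of it (100,000 runs) gave 23%–33%, 36%–51% and 45%–64% for (ii) at 10 per arm, so the equal-variance formula is not the cause of the gap.

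**What would be needed for (ii) at 10 per arm to reach 85%**
- With SD 2 or 2.5, a difference of 2.84 h or 3.54 h: 39% or 49% of 7.3.
- With the differences above, an SD of 1.03 h (1.46 h), 1.34 h (1.90 h) or 1.54 h (2.19 h), all below the stated 2–2.5.
- One-sided 5% is not enough: 35%–47% for 1.46 h and 60%–76% for 2.19 h.

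**Readings that come near the stated range**
- (i), one-sided normal approximation: 87%–97%.
- (i), two-sided paired t on change: 85.8%–96.5% with r = 0.67; 88.8%–97.7% with r = 0.70.
- One SD of change of 1.54 h (r = 0.70 if SD is 2, 0.81 if SD is 2.5) with 2.19 h for both tests: (i) 98%, (ii) 85%. With 1.46 h, the same SD gives (ii) 52%.
- (ii) on change scores with 1.46 h and r of about 0.92: 87%–97%. Test (i) would then be close to 100%, so the range would again not cover both tests.

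**Planned 30 per arm, test (ii), further cases**
- Change scores, 1.46 h: 47%–65% with r = 0.3; 78%–93% with r = 0.67; 82%–95% with r = 0.70.
- Difference detectable with 80% power: 1.47 h (SD 2) to 1.84 h (SD 2.5), which is 20%–25% of 7.3.
- Patients per arm for 80% power (SD 2 / SD 2.5): 31/48 for 1.46 h; 19/29 for 1.90 h.
- If 20% dropped out (my assumption; 24 per arm): 51%–70% for 1.46 h; 73%–90% for 1.90 h.

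**The case against.** The best defence is that the calculation is under-specified rather than wrong. The section calls (i) the primary hypothesis and introduces (ii) only as a further expectation, so the range may have been meant for (i), where a one-sided normal approximation or a correlation near 0.7 nearly recovers it. The SD is attached to the baseline mean, so it may well be cross-sectional, and then 69%–87% for (i) quietly assumes r = 0.5. One reading even hits both ends: an SD of change of 1.54 h with 2.19 h gives 98% and 85%. Enrolment is three times the criticised number, 60 is a minimum, the Benefits section calls this a pilot, and a confidence interval would show what a null result excludes.

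Some of this stands. The sponsor's actual calculation cannot be recovered, the figures for (i) depend on what the SD means, and 30 per arm may be enough for (ii).

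The rest does not remove the problem. If the range belongs to (i) alone, the sham comparison has no power statement. The reading that hits both ends needs an unstated correlation and a between-arm difference other than the stated 20%. Tripling a sample said to give 85%–98%, while citing that calculation as the reason, is itself unexplained. A confidence interval helps after the event but does not justify the size beforehand.

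**Conclusion.** The concern holds. With SD 2–2.5 for the analysed variable, no reading of the 20% that I tried brings (ii) to 85% at 10 per arm. The two-sided figures run from 24% to 64%, and the most favourable one-sided 5% figure is 76%. For either test the published range appears only with assumptions that the plan does not state.

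This does not show that the trial is underpowered. At 30 per arm the answer turns on choices the plan leaves open: short of 80% for 1.46 h unless change scores with a fairly high correlation are used, and above 80% for 1.90 h, in each case before dropout. The conclusion rests on On-time in hours and 5% alpha. The failure at 10 per arm is not sensitive to sidedness. It is sensitive to the SD: analysing change scores with a correlation of about 0.92 would rescue (ii), but the plan states no such thing. The point should be fixed before the sample size is relied on.

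**What to change.** Replace the 10-per-arm sentence with power at 30 per arm, given separately for (i) and (ii). Beside each figure state alpha and sidedness, the hours meant by 20%, whether three-month On-time or change from baseline is analysed, and the SD and any correlation used. For example:

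> With 30 patients per arm and two-sided alpha of __, the two-sample test (ii) has __% power for a difference of __ h in [three-month On-time / change from baseline], assuming SD __ h [and correlation __]. The paired test (i) has __% power for 2.19 h, assuming SD of change __ h.

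If the choices are 1.46 h, SD 2–2.5 for the analysed variable and two-sided 5%, the entry for (ii) is about 60%–79%; other choices give the figures in the working. Then show how 60 follows, with any dropout allowance, or remove the clause that derives 60 from the power analysis.

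The cost is wording only. No patients are added and no test changes. It needs the preliminary-study SD, of On-time or of change, which the sponsor already used. The one downside is that the stated power for the sham comparison may look less favourable.

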## Protocol summary

### **Day 0: Baseline testing (screening):**

- Patient medical history
- General physical exam
- Neurological exam
- Concomitant and PD medications (Levodopa equivalents in mg)
- OFF MDS-UPDRS, part III 12 hour washout of short-acting and 24 hour washout of long acting levodopa containing medications)
- ON MDS-UPDRS, part III (1-2 hours after taking levodopa)
- MOCA and SCOPA
- Clinically trained staff (MD, PA, or RN) will review the consent form in detail with the participant and answer any questions about the study. After consent, the participant will be enrolled in the study and randomized to CR or sham.

- Blinding form – patient
- Blinding form – assessing clinician (MD, PA, RN)

*Surveys to be completed after accepted into study and prior to the 1st day of enrollment. Survey will be completed on medication and sent via email*

1. MDS-UPDRS, Parts I-II, and IV
2. Parkinson's Disease Questionnaire-39 (PDQ-39) scale
3. Schwab and England Activities of daily living score
5. Beck depression and Anxiety inventory

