**Day 1: 1-2 weeks after baseline screening**

- Off Medication UPDRS
- Randomization to CR vs Sham vibrotactile stimulation
- Vibrotactile threshold measurements
- EEG recordings to assess PD-related brain oscillation
- Smell Test
- Comprehensive speech evaluation

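### Randomization is scheduled on both Day 0 and Day 1, with nothing saying which governs; on either date some baseline measures follow allocation

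*Combined protocol and SAP*

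**What the plan says.** The Protocol summary places randomization twice.

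- **Day 0 (screening).** After the examinations, the OFF and ON motor ratings and the cognitive tests, the list turns to consent and then states: "After consent, the participant will be enrolled in the study and randomized to CR or sham". Blinding forms for the patient and the assessing clinician follow directly.
- **Day 1.** This visit is dated "1-2 weeks after baseline screening". Its second item, after the off-medication UPDRS, is "Randomization to CR vs Sham vibrotactile stimulation". Vibrotactile thresholds, EEG, smell test and speech evaluation come below it.

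Two other entries depend on where randomization falls. The baseline questionnaires are described as "Surveys to be completed after accepted into study and prior to the 1st day of enrollment", so they lie between the two dates. At months 3, 6 and 7 patients "will follow the same procedures as enrollment day 1 and 2", and no item is excepted.

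Stimulation first appears on Day 2, after that day's OFF UPDRS and accelerometer recording.

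**The concern.** Two coordinators who both follow the protocol could allocate patients one to two weeks apart. The date decides two things.

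The first is which measures are true pre-allocation baselines. If someone involved in the rating knows or guesses the arm, a baseline taken after allocation can shift differently in the two arms. In a change-from-baseline comparison, such a shift passes straight into the treatment difference. The Study Procedures section has the same clinical staff apply the device and perform the assessments, and the plan does not describe allocation concealment.

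The second is who counts as randomized. Under the Day 0 text, a patient who drops out before Day 1 belongs to the randomized set with an incomplete baseline and no stimulation. The plan defines no analysis population that would settle how to handle that patient.

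**Working it through.** The plan states no figure on this point, so the check is a count. I took every assessment line listed before the first stimulation and classed it as before or after allocation under each placement.

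**Lines counted (Protocol summary)**

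- Day 0, 7 lines: medical history; physical exam; neurological exam; medications with levodopa equivalents; OFF part III; ON part III; MOCA and SCOPA.
- Surveys, 4 lines: MDS-UPDRS I, II and IV; PDQ-39; Schwab and England; Beck inventories.
- Day 1, 5 lines: OFF UPDRS; thresholds; EEG; smell; speech.
- Day 2 before stimulation, 2 lines: OFF UPDRS; accelerometer.

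Total: 7 + 4 + 5 + 2 = 18. The blinding forms are not baseline measures and are left out.

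**Lines after allocation**

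- Day 0 placement: 4 + 5 + 2 = 11, and 11/18 = 61%.
- Day 1 placement, list order taken as time order: 4 + 2 = 6 (thresholds, EEG, smell, speech and the two Day 2 lines), and 6/18 = 33%.
- Day 1 placement, no assumption about order within the day: the two Day 2 lines follow in any case, so at least 2/18 = 11%.

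**Sensitivity to what counts as a baseline line**

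| Lines counted | Day 0 placement | Day 1 placement (list order) |
|---|---|---|
| All 18 | 11/18 = 61% | 6/18 = 33% |
| Without history and the two exams | 11/15 = 73% | 6/15 = 40% |
| Also without the two repeat OFF ratings | 9/13 = 69% | 5/13 = 38% |

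**What is listed before randomization on either date.** The OFF rating, the ON rating ("ON MDS-UPDRS, part III (1-2 hours after taking levodopa"), levodopa equivalents and MOCA/SCOPA all stand above the Day 0 clause. Study Procedures also puts enrollment after baseline screening, which fits that order.

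**What the count cannot cover.** On-time, the outcome tested in Statistical Analysis, comes from the item "Hauser diary to capture OFF time, ON time, ON time with troublesome dyskinesia, sleep time", which is scheduled only in the home-treatment months. With no dated baseline diary, its position relative to allocation cannot be determined. That is a separate gap.

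**How a shift would act.** Write the difference in mean change as (Y1 − B1) − (Y0 − B0), where Y is follow-up, B is baseline, 1 is the real arm and 0 is sham. If knowledge of the arm moves B1 by d and leaves B0 alone, the difference moves by −d. If nobody knows or guesses the arm, d = 0.

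**Loss between Day 0 and Day 1.** The documents give no rate. If 5% to 10% is assumed purely for illustration, the number is 0.05 × 60 = 3 to 0.10 × 60 = 6 patients.

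**The case against.** The strongest reply is that the plan means Day 1. It refers to Days 1 and 2 as the enrollment days, sets the surveys before the first of them, and in Study Procedures puts enrollment after screening. The Day 0 sentence could then be describing what follows consent, with the Day 1 list supplying the date, and all four survey lines would precede allocation. This is a plausible reading. It is not a certain one, because the Day 0 sentence stands in that visit's own list with the blinding forms straight after it.

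The lists are also not strictly chronological. Day 0 shows consent below the examinations, whereas Study Procedures puts consent first. The figure of 6 lines under Day 1 is therefore conditional, and only the two Day 2 lines are firm.

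Finally, blinding is intended and no stimulation is listed before Day 2, so no patient would have felt either chip when these baselines were taken. That stands against any claim that bias has been shown. It does not remove the possibility of staff knowing the arm.

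A reader might also infer that patients are to be randomized again at months 3, 6 and 7, because the cross-reference to Day 1 makes no exception. The documents do not support this. Study Procedures describes one six-month course followed by one month off, and no stimulation is given between months 6 and 7. The word *initially* in Statistical Analysis is unexplained, but no crossover is scheduled. The cross-reference is a drafting slip, though worth correcting.

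**Conclusion.** The point holds as a contradiction in operative text that has a consequence for the design. Randomization has two dates, one to two weeks apart, and nothing ranks them. Under Day 0, 11 of 18 listed baseline lines follow allocation, among them MDS-UPDRS I, II and IV, PDQ-39 and Schwab and England, which the Primary Hypothesis section names as outcomes. Under Day 1, at least 2 lines do, and 6 if list order is time order.

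Three stronger readings should be resisted.

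- That most baselines follow allocation whatever the reading: this is true only under Day 0.
- That every outcome except part III is affected, or that early dropouts have no usable baseline: levodopa equivalents and MOCA/SCOPA are also listed before randomization, and such patients would keep all the Day 0 measures.
- That a definite number of patients would be lost: 3 to 6 follows only from an assumed rate.

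The harm depends on the arm being known or guessed, or on loss between the two days. The plan closes neither route, so the text should be corrected, but nothing shows that the comparison is already biased.

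**What to change.** 1. Delete the randomization clause from the Day 0 list and the randomization item from its present place on Day 1.
2. State one randomization, after the surveys are returned and the pre-stimulation baseline measures are done, and just before the first stimulation of any kind. As the schedule stands, that is Day 2, between the accelerometer recording and the first session. All 18 listed lines then precede allocation.
3. Say whether the Day 1 EEG includes stimulation. Study Procedures intends to study acute stimulation effects by EEG, yet EEG is listed only on Day 1. If stimulation is given then, complete the other pre-stimulation baselines before it and allocate just before it.
4. For months 3, 6 and 7, replace the blanket cross-reference with an explicit list, or except randomization from it.

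The cost is mainly protocol wording, with no added visit or patient. The practical burden is small: devices are programmed individually by USB or SD card, so a chip or card for either arm must be ready for assignment at the visit. If the Day 1 EEG does include stimulation, the baseline accelerometer recording would also have to move ahead of it.
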